## **7. DISCONTINUATION OF STUDY INTERVENTION AND PARTICIPANT DISCONTINUATION/WITHDRAWAL**

### **7.1. Discontinuation of Study Intervention**

It may be necessary for a participant to permanently discontinue study intervention. Reasons for permanent discontinuation of study intervention include the following: ECG changes, adverse events, laboratory abnormalities, potential cases of acute kidney injury or taking of prohibited medications, as described below.

Note that discontinuation of study intervention does not represent withdrawal from the study. If study intervention is permanently discontinued, the participant will remain in the study to be evaluated for safety and PK, if possible. See the [SoA](#) for data to be collected at the time of discontinuation of study intervention and follow-up for any further evaluations that need to be completed.

In the event of discontinuation of study intervention, it must be documented on the appropriate CRF/in the medical records whether the participant is discontinuing further receipt of study intervention or also from study procedures, posttreatment study follow-up, and/or future collection of additional information.

### 7.1.1. ECG Changes

A participant who meets either bulleted criterion based on the average of triplicate ECG readings will be withdrawn from the study intervention.

- QTcF >500 msec.
- Change from baseline: QTcF >60 msec and QTcF > 450 msec.

If a clinically significant finding is identified (including, but not limited to, changes from baseline in QTcF after enrollment), the investigator or qualified designee will determine if the participant can continue in the study and if any change in participant management is needed. This review of the ECG printed at the time of collection must be documented. Any new clinically relevant finding should be reported as an AE.

### 7.1.2. Adverse Events

Treatment will be discontinued and the participant withdrawn from the study for:

- Treatment-related SAEs;
- Other serious or severe AEs, at the discretion of the investigator or sponsor.

### 7.1.3. Laboratory Abnormalities

All of the following laboratory abnormalities require discontinuation if they are confirmed:

- Hyperglycemia: see [Section 6.8.3](#) and [Section 8.2.4.2](#);
- Creatine kinase >10 × ULN;

Note: Urine myoglobin and SCr will be performed as reflex testing for any participant with creatine kinase >10 × ULN.

- AST or ALT that meets ANY of the following:
  - >3 × ULN with at least one total bilirubin value >2 × ULN;
  - >3 × ULN accompanied by signs or symptoms consistent with hepatic injury (eg, new onset elevated PT/INR);
  - Two sequential AST or ALT elevations >5 × ULN, regardless of total bilirubin or accompanying signs or symptoms.

NOTE: See also [Appendix 6](#) for potential cases of drug-induced liver injury.

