#### **8.2.4. Clinical Safety Laboratory Assessments**

See [Appendix 2](#) for the list of clinical safety laboratory tests to be performed and the [SoA](#) for the timing and frequency. All protocol-required laboratory assessments, as defined in [Appendix 2](#), must be conducted in accordance with the laboratory manual and the [SoA](#). Unscheduled clinical laboratory measurements may be obtained at any time during the study to assess any perceived safety issues.

The investigator must review the laboratory report, document this review, and record any clinically relevant changes occurring during the study in the AE section of the CRF. Clinically significant abnormal laboratory findings are those which are not associated with the underlying disease, unless judged by the investigator to be more severe than expected for the participant's condition.

All laboratory tests with values considered clinically significantly abnormal during participation in the study or within 3 days after the last dose of study intervention should be repeated until the values return to normal or baseline or are no longer considered clinically significant by the investigator or medical monitor.

If such values do not return to normal/baseline within a period of time judged reasonable by the investigator, the etiology should be identified and the sponsor notified.

See [Appendix 6](#) for suggested actions and follow-up assessments in the event of potential drug-induced liver injury.

Participants may undergo random urine drug testing at the discretion of the investigator. Drug testing conducted prior to dosing must be negative for participants to receive study intervention (exception may be made for medically prescribed benzodiazepines, see [Section 5.2](#)).

Any remaining serum/plasma from samples collected for clinical safety laboratory measurements at baseline and at all times after dose administration may be retained and stored for the duration of the study. Upon completion of the study, these retained safety samples may be used for the assessment of exploratory safety biomarkers, unexpected safety findings or other internal exploratory purposes. These data will not be included in the CSR. Samples to be used for this purpose will be shipped to either a Pfizer-approved BBS facility or other designated laboratory and retained for up to 1 year following the completion of the study.

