## 10.2. Appendix 2: Clinical Laboratory Tests

The following safety laboratory tests will be performed at times defined in the [SoA](#) section of this protocol. Additional laboratory results may be reported on these samples as a result of the method of analysis or the type of analyzer used by the clinical laboratory, or as derived from calculated values. These additional tests would not require additional collection of blood.

Unscheduled clinical laboratory measurements and/or reflex testing may be obtained at any time during the study at the discretion of the investigator to assess any perceived safety issues.

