**Table 6. Protocol-Required Safety Laboratory Assessments**

Hematology	Chemistry/Other	Urinalysis	At specified times
Hemoglobin Hematocrit RBC count MCV MCH MCHC Platelet count WBC count Total neutrophils (Abs) Eosinophils (Abs) Monocytes (Abs) Basophils (Abs) Lymphocytes (Abs)	BUN/Urea Serum Creatinine a Plasma Glucose (fasting) Calcium Sodium Potassium Chloride Total CO 2 (bicarbonate) AST ALT Total bilirubin Direct bilirubin Indirect bilirubin Alkaline phosphatase Uric acid Albumin Total Bile Acids	pH Glucose (qual) Protein (qual) Blood (qual) Ketones Nitrites Leukocyte esterase Urobilinogen Urine bilirubin Microscopy b	At screening only: 
 
• FSHc
 
• HBsAg
 
• HCVAb
 
• HBcAb
 
• HBsAb
 
• HIV
 
• C-peptided
 
 At times specified in the SoA: 
 
• Urine drug screeninge
 
• Free T4
 
• TSH
 
• Calcitonin
 
• Amylase
 
• Lipase
 
• Lipid profile (ie, total cholesterol, triglycerides, direct HDL, direct LDL)
 

- GFR will be calculated using the MDRD equation:  $GFR (ml/min/1.73m^2) = 175 \times \text{standardized Serum Creatinine} - 1.154 \times \text{age} - 0.203 \times 1.212 [\text{if Black}] \times 0.742 [\text{if female}]$ .
- Only if urine dipstick is positive for blood, protein, nitrites, or leukocyte esterase.
- For confirmation of postmenopausal status in female participants only.
- C-peptide is collected as part of safety laboratory tests at Screening (collected as part of MMTT at other times indicated in [Table 1](#) and [Table 2](#)).
- The minimum requirement for drug screening includes cocaine, THC, opiates/opioids, benzodiazepines, and amphetamines (others are site and study specific).

The investigator must review the laboratory report, document this review, and record any clinically relevant changes occurring during the study in the AE section of the CRF.

Safety/laboratory/analyte results obtained following first dose of the study intervention (Day 1) that could unblind the study (ie, glucose, insulin, glucagon, C-peptide, HbA1c, and PK),

will not be reported to investigative sites or other blinded personnel until the study has been unblinded.

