  - Preexisting AST or ALT baseline values above the normal range: AST or ALT values  $>2$  times the baseline values AND  $>3 \times \text{ULN}$ ; or  $>8 \times \text{ULN}$  (whichever is smaller).
  - Preexisting values of TBili above the normal range: TBili level increased from baseline value by an amount of at least  $1 \times \text{ULN}$  **or** if the value reaches  $>3 \times \text{ULN}$  (whichever is smaller).

Rises in AST/ALT and TBili separated by more than a few weeks should be assessed individually based on clinical judgment; any case where uncertainty remains as to whether it represents a potential Hy’s law case should be reviewed with the sponsor.

The participant should return to the investigator site and be evaluated as soon as possible, preferably within 48 hours from awareness of the abnormal results. This evaluation should include laboratory tests, detailed history, and physical assessment.

In addition to repeating measurements of AST and ALT and TBili for suspected Hy's law cases, additional laboratory tests should include albumin, CK, direct and indirect bilirubin, GGT, PT/INR, total bile acids, and alkaline phosphatase. Consideration should also be given to drawing a separate tube of clotted blood and an anticoagulated tube of blood for further testing, as needed, for further contemporaneous analyses at the time of the recognized initial abnormalities to determine etiology. A detailed history, including relevant information, such as review of ethanol, acetaminophen/paracetamol (either by itself or as a coformulated product in prescription or over-the-counter medications), recreational drug, or supplement (herbal) use and consumption, family history, sexual history, travel history, history of contact with a jaundiced person, surgery, blood transfusion, history of liver or allergic disease, and potential occupational exposure to chemicals, should be collected. Further testing for acute hepatitis A, B, C, D, and E infection, liver imaging (eg, biliary tract), and collection of serum samples for acetaminophen/paracetamol drug and/or protein adduct levels may be warranted.

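### Confirmed creatine kinase above 10 × ULN requires discontinuation, but no scheduled sample is planned to measure creatine kinase

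*Protocol*

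**What the plan says.** Protocol Section 7.1.3 opens its list with "All of the following laboratory abnormalities require discontinuation if they are confirmed". One entry is "Creatine kinase >10 × ULN", followed by a note: "Urine myoglobin and SCr will be performed as reflex testing for any participant with creatine kinase >10 × ULN". CK is the trigger in that note; urine myoglobin and serum creatinine are the follow-on tests.

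Protocol Section 8.2.4 sends the reader to Appendix 2 "for the list of clinical safety laboratory tests to be performed" and to the Schedule of Activities for timing. The chemistry column of Table 6 in Appendix 2 ends with "AST ALT Total bilirubin Direct bilirubin Indirect bilirubin Alkaline phosphatase Uric acid Albumin Total Bile Acids". CK does not appear there or in the haematology, urinalysis or specified-times columns.

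Outside Section 7.1.3 and the abbreviation list, the protocol names CK twice. Section 7.1.4 includes it in the work-up after a second assessment confirms an abnormal serum creatinine. Appendix 6 includes it for suspected Hy's law cases, where "additional laboratory tests should include albumin, CK, direct and indirect bilirubin, GGT, PT/INR" begins the list.

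Appendix 2 also has two general allowances: "Additional laboratory results may be reported on these samples as a result of the method of analysis or the type of analyzer used" and "Unscheduled clinical laboratory measurements and/or reflex testing may be obtained at any time during the study at the discretion of the investigator".

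SAP Section 3.1.2 takes the laboratory tests from the protocol with a Day -1 baseline, and SAP Section 6.2.1.5 lists and summarises them by treatment. Neither names CK.

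**The concern.** Safety laboratory tests are part of the primary endpoint, and Section 7.1.3 presents the CK criterion as compulsory and standing on its own. An investigator or ethics committee reading it would reasonably assume that CK is monitored. If the protocol is followed as written, nothing in the routine schedule produces the number on which the rule acts.

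Two things are at stake. First, a participant without symptoms could exceed the limit without being found, although the protocol says such a participant must stop. Second, the study report could not interpret a zero count: with no planned measurement, absence of the abnormality cannot be told apart from absence of the test.

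**Working it through.** The protocol states no figure for this point and no power or error-rate calculation bears on it. The check is a count and a side-by-side reading.

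**Step 1. Is CK in the required panel?** The chemistry column of Table 6 holds 17 analytes: urea, creatinine, glucose, calcium, sodium, potassium, chloride, bicarbonate, AST, ALT, three bilirubin fractions, alkaline phosphatase, uric acid, albumin and total bile acids (8 + 2 + 3 + 4 = 17). CK among them: 0. CK in the other three columns: 0.

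**Step 2. Could CK be scheduled elsewhere?** Absence from Table 6 is not conclusive alone, because HbA1c is missing from that table but has its own row in the Schedule of Activities. CK has no such row in the readable parts of Tables 1 and 2, and it is not among the screening laboratory exclusions in Section 5.2. Planned CK measurements per participant are therefore 0 at screening, 0 on Day -1, 0 on treatment and 0 at follow-up.

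**Step 3. Is CK treated differently from the other laboratory stops?**

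| Laboratory stop | Triggering analyte | In Table 6 |
|---|---|---|
| Hyperglycaemia (7.1.3, via 6.8.3) | Fasting plasma glucose | Yes |
| Liver (7.1.3) | AST, ALT, total bilirubin | Yes |
| Kidney (7.1.4) | Serum creatinine | Yes |
| Muscle (7.1.3) | Creatine kinase | No |

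CK is the only triggering analyte missing. The order is also inverted: serum creatinine, a reflex test in the CK note, is measured routinely, while the CK that should prompt it is not.

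**Step 4. How else could a CK value arise?** There are four routes, none of them scheduled:

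- *Kidney work-up (7.1.4).* CK is drawn after the second creatinine assessment confirms the abnormality. A second assessment that reaches that section's higher limit already calls for discontinuation.
- *Hy's law work-up (Appendix 6).* For participants with normal baseline values, the entry condition is AST or ALT above 3 × ULN with total bilirubin above 2 × ULN. That combination is itself a stop in Section 7.1.3 once confirmed.
- *Unscheduled test.* At the investigator's discretion.
- *Incidental analyser result.* Depends on the laboratory's equipment.

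The first two routes mostly reach participants who already meet another stop. The last two are permissions rather than a plan.

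**Step 5. Consequence for the analysis.** With no Day -1 value there is no CK baseline. With no planned post-dose values there is no CK summary by treatment and no comparison of active with placebo.

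**The case against.** The strongest reply is that Section 7.1.3 sets out what follows when an abnormality is confirmed; it does not promise that every analyte is scheduled. The same list cites raised PT/INR, which is not in Table 6, and the work-ups call for GGT and phosphate, which are not there either. On that reading the CK entry covers CK found through a work-up, a symptom-driven test or an incidental result. The visible risk table names no muscle risk, so routine CK screening may be a matter of preference.

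Part of this stands. The reading is coherent, but the protocol does not state it. The PT/INR comparison is weak: PT/INR is only an example of a supporting sign for a transaminase criterion whose own analytes are scheduled, whereas CK is a criterion in its own right. The absence of a named muscle risk bears on which resolution the sponsor prefers, not on whether the sections agree.

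A reader might go further and infer that the rule can never be met, that its sensitivity is zero, or that a zero count would be true by construction. The documents do not support this, because all four routes in the working can yield a CK value that engages the criterion. Nor do they support the inference that the study has no muscle-injury data. Muscle symptoms are collected as adverse events, and the scheduled panel includes AST, creatinine, potassium and urine blood, with microscopy when the dipstick is positive.

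**Conclusion.** The point holds in this form: a compulsory discontinuation criterion rests on an analyte that no scheduled sample is planned to measure. Planned CK measurements per participant are 0, against at least one scheduled measurement of every other analyte that triggers a laboratory stop. An asymptomatic rise would not be systematically detected, and a report that no participant met the criterion would be uninformative.

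This is an inconsistency within the protocol that should be corrected. It changes no estimate, sample size or endpoint definition. It rests on the readable text: one row among the blood samples in Table 1 is redacted and its content is unknown. Table 6, which defines the safety panel, shows no redaction.

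**What to change.** Reconcile Section 7.1.3 with Table 6 and the Schedule of Activities so that the criterion and the measured panel agree. Ways to reach agreement include adding CK to the chemistry panel run on samples already drawn (Day -1 among them), stating that the criterion applies only to event-triggered or unscheduled CK, or removing the criterion with its reflex note. Which applies is a clinical decision for the sponsor, and this review does not favour one.

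The cost is small in each case: one analyte line, one clarifying sentence, or one deleted entry, with no new visit. If CK is added, the SAP needs no new method, because its laboratory sections follow the protocol; the downside is incidental rises that need a repeat. If CK stays unscheduled, the report should state how many participants had any CK result, so that a count of those meeting the criterion has a denominator.

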#### **7.1.4. Potential Cases of Acute Kidney Injury**

Abnormal values in SCr concurrent with presence or absence of increase in BUN that meet the criteria below, in the absence of other causes of kidney injury, are considered potential cases of acute kidney injury and should be considered important medical events.

An increase of  $\geq 0.3$  mg/dL (or  $\geq 26.5$   $\mu\text{mol/L}$ ) in SCr level relative to the participant's own baseline measurement should trigger another assessment of SCr as soon as practically feasible, preferably within 48 hours from awareness.

If the second assessment (after the first observations of  $\geq 0.3$  mg/dL [or  $\geq 26.5$   $\mu\text{mol/L}$ ] in SCr relative to the participant's own baseline measurement) is  $\geq 0.4$  mg/dL (or  $\geq 35.4$   $\mu\text{mol/L}$ ), the participant should be discontinued from the study and adequate, immediate, supportive measures taken to correct apparent acute kidney injury.

Participants should return to the investigator site and be evaluated as soon as possible, preferably within 48 hours from awareness of the second assessment confirming abnormal SCr result. This evaluation should include laboratory tests, detailed history, and physical assessment. In addition to repeating SCr, laboratory tests should include serum BUN, serum creatine kinase, and serum electrolytes (including at a minimum potassium, sodium, phosphate/phosphorus, and calcium), in addition to urinary dipstick, urine microscopic examination, and urinary indices. All cases confirmed on repeat testing as meeting the laboratory criteria for acute kidney injury, with no other cause(s) of laboratory abnormalities identified, should be considered potential cases of drug-induced kidney injury irrespective of availability of all the results of the investigations performed to determine etiology of the abnormal SCr. If  $\geq 2$  healthy participants at a given dose level are noted to have 2 consecutive SCr results of  $\geq 0.3$  mg/dL (or  $\geq 26.5$   $\mu\text{mol/L}$ ), an assessment of whether the finding may be considered an adverse drug reaction should be undertaken.

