**Table 3. Completed and Ongoing Clinical Studies**

Study Identifier	Study Design and Type of Control	Dosing Regimen, Formulation Dose	Number of Participants Randomized	Population	Treatment Duration	Study Status
C3991001	Phase 1, double-blind, randomized, placebo controlled, single ascending dose study. Two interleaving cohorts of healthy adult participants with crossover, placebo substitution design.  One cohort of healthy adult Japanese participants with crossover placebo substitution design.	PF-07081532 or placebo.  Orally administered solution  Dose Range: 10 mg to 200 mg	PF-07081532: 22 Placebo: 12	Healthy Adult Participants	Single dose	Completed
C3991002	Phase 1, randomized, double-blind (investigator- and participant-blind), sponsor-open, placebo-controlled, multiple oral dose-escalating study.	Orally administered tablet	Part A: 10 (8 PF-07081532: 2 placebo) planned participants/cohort		Multiple doses	Ongoing: dosing completed, data analysis and reporting ongoing
		Target dose range: PF-07081532 10 mg to 180 mg or placebo		Adult Participants with T2DM	28 days' dosing	
		Target dose PF-07081532 180 mg or placebo	Part B: 15 (12 PF-07081532: 3 placebo) planned participants/cohort	Adult Participants with Obesity	42 days' dosing	
		Target dose PF-07081532 180 mg or placebo	Part C: 10 (8 PF-07081532: 2 placebo) planned participants/cohort	Adult Participants with T2DM	42 days' dosing	

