### 4.2.1. Population(s)

Participants enrolled in this study will be adults with inadequately controlled T2DM (as indicated by HbA1c at screening) on metformin monotherapy, which is considered first-line therapy for glycemic control according to current treatment guidelines. At screening, this study requires that participants with T2DM have been taking a minimum stable metformin dose of at least 500 mg/day for at least 2 months prior to the screening visit. The dose of metformin, where possible, is expected to remain the same until completion of study participation (ie, follow-up visit). Available in vitro data suggest that PF-07081532 is not expected to impact the PK of metformin via inhibition of OCT2, and the risk of a clinical interaction is deemed negligible. One or more cohorts of non-diabetic participants with obesity may be enrolled in this study. The safety, tolerability, PK and PD data collected in this study may be used to select doses and dosing scheme algorithms for future studies of PF-07081532.

The population planned for this study will be male and female adult participants. Female participants will be WONCBP, since at the present time embryofetal development toxicity studies with PF-07081532 have not been conducted. In male participants appropriate measures are expected to be followed to limit potential transfer of PF-07081532 in semen to partners (see [Appendix 4](#)).

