### Type of Participant and Disease Characteristics:

3. Patients with T2DM who are treated with metformin.

**Note:** Participants must be taking metformin monotherapy as their only anti-hyperglycemic treatment. Metformin dose must be at least 500 mg per day and must be stable, defined as no change in the treatment and participant-reported compliance with treatment, for at least 2 months prior to the screening visit.

4. HbA1c  $\geq 7.0\%$  and  $\leq 10.5\%$  at screening (confirmed by a single repeat, if necessary).

**Note:** For non-diabetic participants with obesity (if enrolled), HbA1c  $< 6.5\%$  at screening.

5. Participants who are willing and able to comply with all scheduled visits, treatment plan, laboratory tests, lifestyle considerations, and other study procedures.

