### Medical Conditions:

1. Evidence or history of clinically significant hematological, renal, endocrine, pulmonary, gastrointestinal, hepatic, psychiatric, neurological, dermatological, or

- allergic disease (including drug allergies but excluding untreated, asymptomatic, seasonal allergies at the time of dosing).
- Participants who have chronic conditions other than T2DM and obesity (for example, hypercholesterolemia or hypertension) but are controlled by either diet or stable doses of 2 or fewer medications may be included (for example, a participant with hypercholesterolemia on appropriate treatment is eligible). See [Section 6.8](#) for further information on concomitant medications.
  - For non-diabetic participants with obesity (if enrolled), a medical history of T2DM.
2. Diagnosis of type 1 diabetes mellitus or secondary forms of diabetes.
  3. Evidence or history of clinically significant cardiovascular disease. In particular, history of myocardial infarction, unstable angina, arterial revascularization, stroke, New York Heart Association Functional Class II-IV heart failure, or transient ischemic attack within 6 months of screening.
  4. Any malignancy not considered cured (except basal cell carcinoma and squamous cell carcinoma of the skin); a participant is considered cured if there has been no evidence of cancer recurrence in the previous 5 years.
  5. Acute pancreatitis or history of chronic pancreatitis.
  6. Acute gallbladder disease.
  7. Any condition possibly affecting drug absorption (eg, prior bariatric surgery, gastrectomy, or any area of intestinal resection, active inflammatory bowel disease or pancreatic insufficiency).
  8. Personal or family history of MTC or MEN2, or participants with suspected MTC per the investigator's judgement.
  9. Other medical or psychiatric condition including recent (within the past year) or active suicidal ideation/behavior or laboratory abnormality that may increase the risk of study participation or, in the investigator's judgment, make the participant inappropriate for the study.

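### The dose-level creatinine prompt in Protocol Section 7.1.4 is tied to healthy participants, whom none of the three planned cohorts enrols (low impact)

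*Protocol*

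**What the plan says.** Protocol Section 7.1.4 handles serum creatinine (SCr) at two levels.

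- **Individual level.** A rise of ≥0.3 mg/dL (≥26.5 µmol/L) relative to the participant's "own baseline measurement should trigger another assessment of SCr as soon as practically feasible". If the second assessment is ≥0.4 mg/dL (≥35.4 µmol/L), the participant should be discontinued and evaluated. Cases confirmed on repeat testing with no other cause count as potential drug-induced kidney injury. These rules speak of the participant or of participants, without qualification.
- **Dose level.** The last sentence calls for an assessment of a possible adverse drug reaction if at least 2 "healthy participants at a given dose level are noted to have 2 consecutive SCr results of" ≥0.3 mg/dL.

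On who is enrolled, Section 4.2.1 says "Participants enrolled in this study will be adults with inadequately controlled T2DM (as indicated by HbA1c at screening) on metformin monotherapy", and adds that "One or more cohorts of non-diabetic participants with obesity may be enrolled in this study". Inclusion criterion 3 in Section 5.1 reads "Patients with T2DM who are treated with metformin". The notes to criteria 4 and 6 make separate provision for non-diabetic participants with obesity, and for no other group.

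**The concern.** The individual rules look at one person at a time. The last sentence is the only place where the section asks whether a pattern across participants at one dose points to the drug. If it names a population that the study does not recruit, two participants with T2DM at the same dose could both show confirmed creatinine rises without meeting the condition as written.

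That matters somewhat here. Safety is the primary objective, no data monitoring committee is used (Section 10.1.3.1), and doses in later cohorts may be adjusted on emerging data (Section 4.1). Section 2.3 also names dehydration as a possible consequence of severe gastrointestinal reactions, so a renal prompt is not idle in this setting.

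**Working it through.** The plan gives no figure to reproduce. The check compares texts, with a simple count at the end.

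**1. Who is in the study.** Section 4.1 plans 3 cohorts of about 12 participants with T2DM (9 active, 3 placebo each) and allows up to 3 more. One or more cohorts may be in non-diabetic participants with obesity. No third population is provided for.

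**2. What healthy means in these documents.** The word is not defined. As a population label it belongs to the earlier single-dose study in Table 3: "Two interleaving cohorts of healthy adult participants with crossover, placebo substitution design". The same table lists adults with T2DM and "Adult Participants with Obesity" as separate populations of the multiple-dose study. Exclusion criterion 1 in Section 5.2 refers to "Participants who have chronic conditions other than T2DM and obesity (for example, hypercholesterolemia or hypertension"), which places T2DM and obesity among chronic conditions. Neither document calls a participant in this study healthy, apart from the sentence at issue.

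**3. Coverage of the prompt, read literally.**

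- Planned cohorts: 3 × 12 = 36 participants, all with T2DM. Covered: 0.
- If all optional cohorts run: 6 × 12 = 72 participants. If all three optional cohorts were in obesity, 3 × 12 = 36 of these could be covered on a generous reading of healthy; otherwise fewer, or none.

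**4. Whether another rule does the same job.** Section 7.1.3 (laboratory discontinuation criteria), Section 9.4 (sponsor-open review) and SAP Sections 3.1.2 and 6.2.1.5 (laboratory data) set no two-participant creatinine trigger. I found none elsewhere in either document.

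**5. How the three creatinine thresholds in Section 7.1.4 are expressed.**

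- Retest, ≥0.3 mg/dL: stated as an increase relative to the participant's own baseline.
- Discontinuation, ≥0.4 mg/dL: the baseline reference sits in the parenthesis describing the first observation and is not attached to the 0.4 threshold.
- Dose-level prompt, ≥0.3 mg/dL: stated as a result, with no baseline reference.

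Only the first is explicit. The other two need the reader to carry the baseline reference forward.

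**The case against.** The case for leaving the sentence alone has four parts.

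- **Little is lost.** This stands. Each confirmed, unexplained case already counts as potential drug-induced kidney injury, with no minimum of two. A laboratory abnormality that needs further testing is recorded as an AE (Section 10.3.1), and causality is assessed for every AE (Section 10.3.3). Safety issues go to the sponsor immediately (Section 8), and safety laboratory data are reviewed on an ongoing basis (Section 9.3.2). Some sponsor staff are unblinded for real-time review (Section 4.2.3). None of this is a fixed two-participant trigger, but detection does not depend on the prompt.
- **The prompt is advisory.** This also stands. It says that an assessment should be undertaken when the condition is met. It does not confine assessment to that case, and it stops no dosing.
- **Participants with obesity could be called healthy.** This stands in part. They would have HbA1c below 6.5%, eGFR of at least 60 mL/min/1.73m² and no clinically significant organ disease. Table 3 and exclusion criterion 1 point the other way, but without a definition the matter is arguable. It does nothing for the T2DM cohorts.
- **Context supplies the baseline reference.** A site would probably read 0.3 mg/dL as a rise throughout. If so, the same courtesy applies to the 0.4 mg/dL threshold; if not, both sentences need mending. Either way they should be treated alike.

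**Conclusion.** The sentence is wrong as written, with low impact. Read literally, the dose-level prompt covers 0 of about 36 planned participants and, at most arguably, participants in any obesity cohort. What is lost is that one fixed prompt.

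The count assumes that the three planned cohorts enrol participants with T2DM, as Section 4.1 describes, and that healthy carries the meaning it has in Table 3. No event rate is estimated, because the documents give none.

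A reader might infer more, and three stronger readings are not supported:

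- *The prompt can apply to nobody, whichever cohorts run.* This is secure only for T2DM participants, because healthy is undefined.
- *Renal safety monitoring is missing.* The individual rules and sponsor review cover every participant.
- *T2DM participants were left out on purpose.* No rationale is given, and the rest of the section is unqualified. Carried-over wording is the likelier explanation, though that is an inference.

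**What to change.** Replace the last sentence of Section 7.1.4 with: *If ≥2 participants at the same dose level each have 2 consecutive SCr increases of ≥0.3 mg/dL (≥26.5 µmol/L) from their own baseline, the possibility of an adverse drug reaction should be assessed.*

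In the same edit, make the discontinuation rule explicit: the second assessment must show *an increase of ≥0.4 mg/dL (≥35.4 µmol/L) from the participant's own baseline*. All creatinine thresholds in the section are then stated as changes from baseline. Deleting the word healthy alone would leave the baseline reference missing from two of the three.

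The cost is two sentences in one section, made by a protocol amendment with IRB/EC approval (Section 10.1.1), which can be combined with any other amendment. Sample size, endpoints, visit schedule, SAP analyses and the numerical thresholds stay as they are. The SAP version history mentions a data review before database release, so dosing may already be over; if so, the corrected wording should go into the next protocol that reuses this section.
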